#### **TRIAL SCHEMA**

#### TRIAL SUMMARY

Title

Efficacy and safety of first line Cemiplimab in advanced BCC: A phase 2 trial (IMPACT)

Objective

To evaluate the benefit and safety of cemiplimab, a fully human anti-PD-1 monoclonal antibody in patients with locally advanced BCC

**Endpoints** 

#### Primary:

To assess the objective response rate (ORR) of cemiplimab in patients with locally advanced BCC at 6 months, by independent central review.

#### Secondary:

- To evaluate safety and tolerability including the frequency, severity and relatedness of adverse events (AEs) to the study treatment. AEs will be assessed according to CTCAE v5.0.
- To assess ORR: Proportion of patients having achieved partial (PR) or complete (CR) remission at 12 and 24 months.
- To assess disease control rate (DCR) at 6, 12 and 24 months. DCR is ORR plus stable disease (SD)
- To assess progression-free survival (PFS) defined as the time from registration to the first of one of the following: development of clinical/radiological disease progression (composite criteria/RECIST 1.1) or death from any cause.
- To assess overall survival (OS) defined as time from registration to the date of death from any cause.
- To assess patient health status and quality of life (QoL) using the patient reported outcome measures EQ-5D-5L, EORTC QLQ-C30, Skindex-16, FNAE and the Hornheide questionnaire.

Trial Design

Open label, single arm, two stage, phase II non-randomised multi-centre trial

Type and number of patients

41 patients with locally advanced BCC will be recruited

#### Treatment

Up to 34 cycles of treatment with cemiplimab alone (maximum of 24 months of treatment)

#### Main inclusion criteria

- Aged 18 years or over
- Histologically proven locally advanced BCC
- ECOG performance status 0 or 1
- Adequate renal, liver and bone marrow function
- At least 1 measurable target lesion

#### Main exclusion criteria

- Eligible for curative surgical treatment
- Eligible for curative radiation treatment
- Contraindication to immunotherapy

Please refer to pages 11-14 for the full inclusion and exclusion criteria.

#### 1 BACKGROUND

Basal cell carcinoma (BCC) is the most common type of skin cancer worldwide. Risk factors for the development of BCC include fair skin type, exposure to ultraviolet radiation, age, history of BCC, genetic disorders (e.g., Gorlin syndrome, xeroderma pigmentosum), and immunosuppression (1). BCC tumours are generally slow growing and rarely metastasize, and the prognosis for patients who receive appropriate therapy is typically very good (2, 3). The most common treatment strategies are surgery, radiotherapy, topical treatments and photodynamic therapy (PDT).

In a small proportion of patients, BCCs can progress to an advanced stage (aBCC), including locally advanced BCC (laBCC) and metastatic BCC (mBCC) which become more difficult to treat. LaBCCs are large, aggressive, or recurrent tumours or those that penetrate deeper into the underlying skin and surrounding tissues (4, 5). LaBCCs may not be amenable to radiotherapy and can be challenging to treat effectively with surgery without causing significant morbidity, loss of function, or disfigurement when they are located in a difficult-to-treat area (e.g. periorbital) (4). LaBCCs are also associated with a high risk of recurrence (4, 5). Metastatic disease is rare, occurring in only 0.0028–0.55% of BCCs, and arises more frequently with primary tumours that are large, untreated, or aggressive or with recurrent tumours (6). The most frequent sites of metastasis are the bone, lung, liver and regional lymph nodes.

The proposed criteria to help define when surgery and irradiation are inappropriate are:

- >5 BCCs, if patient suffers from genetic syndromes
- BCC >10 mm, relapsing after 2 surgeries in critical locations (e.g. periocular and perioral areas)
- BCC infiltrating in bone/cartilage/other structures and curative resection unlikely
- Relapsing BCC after multiple surgeries and/or radiotherapy
- Advanced BCC in patients who do not qualify for general anaesthesia

In an attempt to facilitate appropriate management of patients with IaBCC, several experts have proposed guidelines for defining IaBCC (4, 7). Lear et al, suggested that BCCs should be defined as locally advanced if they are stage II or above according to the American Joint Committee on Cancer guidelines and if current treatment options are contraindicated by disease- or patient-driven factors (4). The disease-driven factors contributing to a diagnosis of IaBCC include tumour size, location in mask area, higher number of BCCs, aggressive histological and recurrent disease with reduced chance of cure. Patient-driven factors contributing to a diagnosis of IaBCC include young age where radiotherapy is discouraged, poor performance status, loss of cosmesis affecting quality of life, patient not inclined for treatment, and patients with genodermatoses (e.g. Garlin syndrome, xeroderma pigmentosum) or the presence of immunosuppression (4).

Aberrations in the hedgehog pathway are significant in the pathophysiology of BCC (8), and two licensed hedgehog pathway inhibitors (HHIs), vismodegib (based on ERIVANCE study: (9) and sonidegib (based on BOLT study: (10) have been approved for the treatment

of laBCC in cases where surgery and radiotherapy are inappropriate and in symptomatic metastatic BCC.

In clinical trials of hedgehog pathway inhibitors for laBCCs, objective response rates are estimated at 45%, with a median duration of response of 9.5 months (9, 11). Development of resistance is common, cures are rare, and adverse effects can be bothersome, leading to dosing interruptions or drug discontinuation (12).

BCC has one of the highest rates of somatic mutations among all cancer types because of effects of ultraviolet radiation (13), suggesting sensitivity to anti-programmed cell death 1 (PD-1) T-cell inhibition like other highly ultraviolet-mutated tumours. Small series have reported clinical activity of PD-1 inhibitors as second line treatment in both IaBCC and mBCC (14-16). Small nonrandomized trials also showed efficacy of second-line pembrolizumab (17) and trials of second-line cemiplimab have been successful (18). Indeed, cemiplimab has been licensed as a second line treatment in patients who progress with or are intolerant to hedgehog pathway inhibitors.

In the UK, NICE has appraised that vismodegib is not recommended within its marketing authorisation for treating symptomatic mBCC, or laBCC that is inappropriate for surgery or radiotherapy, in adults because of the uncertainty in the evidence and because it is not cost effective (https://www.nice.org.uk/guidance/ta489/chapter/1-Recommendations). To date sonidegib has not been appraised by NICE. Hence, there is no valid, effective first-line treatment option for patients with laBCC or mBCC in the UK. Recently there has been a case series of 2 cases treated with nivolumab and pembrolizumab as first-line therapy in laBCC showing impressive responses (19). The potential advantages to using anti-PD-1 over hedgehog pathway inhibitors include improved medication compliance (intravenous route of administration) and the potential for long-term durable responses including complete responses. This suggests that anti-PD-1 therapy may be a feasible frontline therapeutic option in patients with advanced BCC.

Hence, we propose to evaluate the safety and efficacy of first line cemiplimab in patients with advanced BCC in this phase II trial.

#### 2 AIMS OF THE STUDY

#### 2.1 Hypothesis

Administration of the immunotherapy cemiplimab is well tolerated in patients with locally advanced basal cell carcinoma (laBCC) who will benefit from administration of cemiplimab with a response to treatment.

#### 2.2 **Primary endpoint**

To assess objective response rate (ORR) of cemiplimab in laBCC at 6 months, by independent central review.

ORR is defined as proportion of patients achieving a complete response (CR) or partial response (PR).

Clinical response criteria (see Appendix 2 table 1) will be used to determine ORR, for externally visible tumour(s) that require bidimensional measurements according to World Health Organization (WHO) criteria. Composite response criteria (see Appendix 2 table 2) will be used for patients who have both target lesions measurable by clinical response criteria and radiologically by RECIST 1.1 to determine ORR.

In patients achieving CR, histological assessment of tumour biopsies will be required to confirm CR, otherwise this will be reported as PR.

# 2.3 Secondary endpoints

- To evaluate safety and tolerability including the frequency, severity and relatedness of AEs to the study treatment. AEs will be assessed according to CTCAE v5.0.
- To assess ORR at 12 months and 24 months.
- To assess disease control rate (DCR) at 6, 12 and 24 months. DCR is ORR plus stable disease (SD).
- To assess progression-free survival (PFS) defined as the time from registration to the first of one of the following: development of clinical/radiological disease progression (composite criteria/ RECIST 1.1) or death from any cause.
- To assess overall survival (OS) defined as time from registration to the date of death from any cause.
- To assess patient health status and quality of life (QoL) using the patient reported outcome measures EQ-5D-5L, EORTC QLQ-C30, Skindex-16, FNAE and the Hornheide questionnaire.
- To estimate the time to response (TTR: defined as the time from the start of treatment to the first objective tumour response (tumour shrinkage of ≥30%)) and duration of response (DOR: the time from response to progression/death) to cemiplimab.

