### **Documentation of New Lesions**

 The presence of a new lesion should be unequivocal: i.e. not attributable to differences in scanning technique, change in imaging modality or findings thought to represent something other than tumour (for example, some 'new' bone lesions may be simply healing or flare of pre-existing lesions). • A lesion identified at a follow-up visit in an anatomical location that was not scanned at baseline is considered a new lesion and will indicate disease progression.

Response Criteria	Evaluation of target lesions
* Complete Response (CR):	Disappearance of all target lesions. Pathological lymph nodes (whether target or non-target) must have reduction in short axis to <10mm.
* Partial Response (PR):	At least a 30% decrease in the sum of the LD of target lesions, taking as reference the baseline sum LD
* Progressive Disease (PD):	At least a 20% increase in the sum of the LD of target lesions, taking as reference the smallest sum LD recorded since the treatment started or the appearance of one or more new lesions. In addition, the smallest sum LD must also demonstrate an absolute increase of at least 5mm.
* Stable Disease (SD):	Neither sufficient shrinkage to qualify for PR nor sufficient increase to qualify for PD, taking as reference the smallest sum LD since the treatment started
	Evaluation of non-target lesions
* Complete Response (CR):	Disappearance of all non-target lesions and normalization of tumour marker level
*Non-CR/non-PD:	Persistence of one or more non-target lesion(s) or/and maintenance of tumour marker level above the normal limits
* Progressive Disease (PD):	Unequivocal progression of existing non- target lesions (1). The appearance of one or more new lesions is also considered progression.

 Although a clear progression of "non target" lesions only is exceptional, in such circumstances, the opinion of the treating physician should prevail and the progression status should be confirmed later on by the review panel (or study chair).

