## Duration of overall response

 The duration of overall response is measured from the time measurement criteria are met for CR or PR (whichever status is recorded first) until the first date that recurrence or PD is objectively documented, taking as reference for PD the smallest measurements recorded since the treatment started.

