# APPENDIX 2: CLINICAL AND COMPOSITE RESPONSE CRITERIA FOR PATIENTS WITH ABCC

These criteria are designed for externally visible lesions that can be measured bidimensionally using digital medical photography. This appendix also provides clinical and composite response criteria for disease that is measureable by both clinical response criteria and RECIST 1.1.

Patients will be followed by digital medical photography and also undergo radiologic imaging (MRI/CT scan) at baseline, and this will also be performed serially at each response assessment unless the investigator deems that baseline radiologic imaging was uninformative. Radiologic imaging will be essential in the evaluation of tumours that have subdermal components that cannot be adequately assessed by digital medical photography. Standardised digital photographs of the externally visible component of all target lesions must be obtained at baseline and at the time of each subsequent tumour assessment. Investigators will also provide a clinical description of the externally visible target lesion(s) at baseline and at each tumour assessment, as well as comments on any changes in the lesion(s) since the previous assessment.

For target lesions that are measured by digital medical photography, measurements will be bi-dimensional.

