# **Clinical Response Criteria for Externally Visible Tumours**

# A. Externally Visible Tumour Dimension

The externally visible component of target lesion(s) will be measured using bi-dimensional WHO criteria as the sum of the products (of individual target lesions) in the longest dimension and perpendicular second longest dimension – at each tumour assessment and will be documented using standardised digital photography. In the absence of substantial change in lesion geometry, subsequent visit measurements should be performed in the same axes and the investigator should refer to the previous visit's annotated photographs as a starting point to identify axis for measurement when making subsequent assessments.

Clinical response criteria for externally visible tumour(s) require bi-dimensional measurements according to WHO criteria, and are as follows:

- Complete response of externally visible disease (vCR): all target lesion(s) and non-target lesions no longer visible, maintained for at least 4 weeks. Documentation of vCR requires confirmation by biopsies of site(s) of externally visible target lesion(s) with histologic confirmation of no residual malignancy. In the absence of such histologic confirmation, a patient cannot be deemed to have experienced vCR and the best response would be partial response.
- Partial response of externally visible disease (vPR): decrease of 50% (WHO criteria) or greater in the sum the products of perpendicular longest dimensions of target lesion(s), maintained for at least 4 weeks
- Stable externally visible disease (vSD): not meeting criteria for vCR, vPR, or progressive disease
- Progression of visible disease (vPD): increase of ≥25% (WHO criteria) in the sum of the products of perpendicular longest dimensions of target lesion(s). In rare cases, unequivocal progression of a non-target lesion may be accepted as vPD.

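### Time to response is triggered by a 30% shrinkage with no stated scale; photographed lesions need a 50% fall in the product of diameters, so a patient scored as stable disease can be given a response time

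*Protocol*

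**What the plan says.** Protocol section 2.3 gives one TTR definition for every patient: from the start of treatment to the "first objective tumour response (tumour shrinkage of ≥30"%). It names no scale and does not limit the figure to lesions measured on MRI or CT. The same sentence defines DOR as "the time from response to progression/death" and says nothing more about when response begins. Section 11.4 adds no start date.

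The response criteria are set elsewhere and depend on how the lesion is measured:

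- **Radiology (Appendix 1, RECIST 1.1).** PR is "At least a 30% decrease in the sum of the LD of target lesions".
- **Photography (Appendix 2).** "For target lesions that are measured by digital medical photography, measurements will be bi-dimensional". PR is a "decrease of 50% (WHO criteria) or greater in the sum the products of perpendicular longest dimensions", maintained for at least 4 weeks. Stable disease is the remainder: "not meeting criteria for vCR, vPR, or progressive disease".
- **Both (Appendix 2, Table 2).** The clinical and RECIST results are combined into a composite response.
- **Extensively ulcerated lesions (Appendix 2, C).** CR is re-epithelialisation held for at least 4 weeks, and there is no PR category.
- **Surgery (Appendix 2, Composite Response Criteria).** Clear margins on all target lesions that were previously inoperable count as PR.

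Section 2.2 defines ORR as the proportion with CR or PR. Appendix 1, under Duration of overall response, has duration "measured from the time measurement criteria are met for CR or PR".

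**The concern.** A single percentage is applied across several response scales, and it belongs to only one of them. Thirty per cent is the PR threshold for a sum of longest diameters. For a photographed lesion, a 30% fall in the quantity that the protocol measures is stable disease.

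Applied literally, the parenthesis lets TTR start in a patient who is not a responder for the ORR. DOR may follow if its starting point is read in the same way. The ulcerated-lesion and surgical routes work in the opposite direction: they produce responders with no 30% shrinkage date to record. ORR, TTR and DOR could then describe different sets of patients.

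Durability matters to this trial's argument. The Background cites a median DOR of 9.5 months for hedgehog inhibitors and names durable response as a potential advantage of anti-PD-1 treatment.

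**Working it through.** **Inputs.** TTR trigger: 30%, scale unstated (section 2.3). PR for photographed lesions: product down by at least 50% (Appendix 2, A). RECIST PR: sum of longest diameters down by at least 30% (Appendix 1). Assessment interval: 12 weeks, plus or minus 7 days (section 6.5.1).

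**Formula.** For one lesion, or for several shrinking alike, let a and b be the fractional falls in the longest and perpendicular diameters. Then

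fall in product = 1 − (1 − a)(1 − b).

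**Reading 1: 30% of the product.** This is the scale set for photographed lesions. Every fall from 30% to just under 50% is stable disease for ORR but meets the TTR trigger. With equal shrinkage in both axes:

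- 30% of the product is 1 − √0.70 = 16.3% per diameter.
- 50% of the product is 1 − √0.50 = 29.3% per diameter.

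**Reading 2: 30% of the longest diameter only (a = 0.30).**

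| Fall in perpendicular | Fall in product | Score on photography |
|---|---|---|
| 0% | 1 − 0.70 × 1.00 = 30% | stable disease |
| 10% | 1 − 0.70 × 0.90 = 37% | stable disease |
| 20% | 1 − 0.70 × 0.80 = 44% | stable disease |
| 28.6% | 50% | PR size threshold reached |

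The break-even value is b = 1 − 0.50/0.70 = 28.6%. Below it, the TTR trigger is met and the PR threshold is not.

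**Reading 3: 30% in both diameters.** The product falls 1 − 0.70² = 51%, so a lesion that meets the trigger also meets the PR size threshold. The size mismatch disappears. The 4-week maintenance is still missing from the trigger.

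**Who is exposed under readings 1 and 2.** Patients judged by photography alone, and composite patients whose RECIST result is stable disease or not applicable. In Table 2, clinical stable disease with RECIST PR is already a composite PR. Patients followed only on MRI or CT are scored by RECIST, where the threshold is 30%.

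**Who could be missed.** An ulcerated-lesion CR is defined by re-epithelialisation, and a surgical-clearance PR by margins. Neither supplies a 30% shrinkage date.

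**Size per patient.** A responder who passes 30% one visit before meeting PR has TTR about 12 weeks shorter and DOR about 12 weeks longer. Twelve weeks is 12 × 12/52 = 2.8 months, and 2.8/9.5 = 29% of the hedgehog-inhibitor median cited in the Background. This is a shift for one such patient, not for the median.

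**The case against.** The strongest defence is that the trigger is an objective tumour response and the 30% is only a gloss. Section 6.5.1 uses that term for what is assessed under the clinical, RECIST or composite criteria, and section 2.2 makes ORR mean CR or PR. Read that way, a patient with stable disease has no objective response and gets neither TTR nor DOR. This stands far enough that one can say only that such a patient *can* be given a TTR, not that every such patient will be. It does not rescue the parenthesis, which is then a wrong gloss for photographed lesions.

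A reader might infer more than the protocol supports on four points:

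- **That section 2.3 contradicts Appendix 1 on DOR.** It does so only if the TTR parenthesis is carried into the DOR clause. Otherwise Appendix 1 supplies the start date that section 2.3 leaves open.
- **That composite responses never rest on 30%.** They sometimes do: RECIST PR decides the composite result when the clinical result is stable disease or not applicable.
- **That median TTR is too short and median DOR too long.** The direction is clear only for responders who cross 30% before PR. Adding patients who never reach PR, or losing ulcerated-lesion responders, could move the medians either way.
- **That most patients are exposed.** Appendix 2 says even deeply invasive tumours will generally be measured by photography. It also provides for serial imaging unless the baseline scan was uninformative, whereas section 6.2 limits on-treatment scans to those following target lesions. No split is given.

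TTR and DOR are also secondary, are not in the trial summary's list, and have no stated hypothesis test. That limits the stakes. Leaving the matter to an analysis plan is not a full answer, because the protocol already states a numerical rule that does not fit its own criteria.

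**Conclusion.** The point holds as a mismatch between a stated endpoint rule and the protocol's own response criteria. The 30% in section 2.3 has no scale and matches only RECIST. For photographed lesions, a product fall from 30% to under 50% (16.3% to under 29.3% per diameter with equal shrinkage) is stable disease for ORR yet can start TTR. It can start DOR as well if response has the same meaning in both clauses. The same follows for a 30% fall in the longest diameter when the perpendicular falls by less than 28.6%.

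This rests on the parenthesis being applied literally and on one of those two readings; it fails if 30% in both diameters is meant. The shift is about 12 weeks for each responder who passes 30% one visit before PR. The number of such patients and the net effect on the medians cannot be derived from the protocol. ORR, the two-stage decision rule and the sample size are untouched. It should be corrected, as a fault in two secondary endpoints.

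**What to change.** In section 2.3, delete the parenthesis giving the 30% shrinkage. Define TTR, in ORR responders only, as the time from first dose to the first assessment at which CR or PR is met under whichever criteria score that patient's ORR: clinical, RECIST 1.1, composite, ulcerated-lesion or surgical-clearance. Require that the response is later maintained or confirmed as Appendices 1 and 2 demand, but date it to that first assessment. Start DOR on the same date, which brings section 2.3 into line with Appendix 1.

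The cost is a short wording change. It needs no new visits or measurements and leaves ORR and the sample size as they are.

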#### 2.4 Translational Objective

Patient tissue samples, previously collected as part of the patient's standard of care, will be collected for evaluation of PD-L1 immunohistochemistry, TMB assessments, or MHC-I immunohistochemistry and correlation with efficacy analyses.

